## 8.2. Background Characteristics

### 8.2.1. Participant Disposition

The analyses of participant disposition will use all participants who provided written informed consent to the study, or for whom consent was given by a proxy.

The summaries of participant disposition will include the number of participants who were screened, who were not randomized and reasons for not having been randomized, who were randomized, who received IP, who did not receive IP, the number and percentage of participants who completed the study, who prematurely withdrew from the study, primary reasons for not completing the study, who completed treatment, who discontinued treatment prematurely, including primary reasons for discontinuing treatment, and who discontinued treatment but completed study. For participants completed/discontinued the treatment, percentages will be calculated based on the number of participants who received IP in the randomized group. Other percentages will be calculated based on the participants who were randomized; treatment assignment will be taken as planned.

A completer for the study is defined as one who completed the last follow up visit (Visit 11, Day 28±3) based on the study completion case report form (CRF) page with the completion question answered Yes.

A participant is marked as completing the treatment if the complete treatment question on the study treatment completion CRF page is answered Yes.

The number of participants in each analysis set will be provided. Using Randomized Set, the reason for not being included in other analysis sets will be summarized.

Screen failure participants will be listed in a data listing.

### **8.2.2. Protocol Deviations**

Protocol deviations identified during the study will be captured and categorized by the study team review as major or minor deviations in blinded fashion on an ongoing basis until database lock.

The major protocol deviations will be summarized for all randomized participants using the FAS. All protocol deviations (major and minor) will be included in a data listing.

### **8.2.3. Demographics and Baseline Characteristics**

The following analyses will be provided separately for the Safety Analysis Set (using actual treatment received), and the FAS (using randomized treatment).

Demographic data (age at informed consent date, race, sex, ethnicity) and baseline characteristics, such as height, weight, and body mass index (BMI), will be summarized by treatment group (randomized for FAS and actual for Safety Analysis Set) and overall.

### **8.2.4. Pregnancy Tests**

A serum or urine pregnancy test will be conducted for all female participants at screening. These data will be listed by participant.

### **8.2.5. Medical/Surgical History**

Listings and tabulations associated with Medical and/or Surgical History will use the Safety Analysis Set.

Medical/surgical history collected at screening will be coded using the Medical Dictionary for Regulatory Activities (MedDRA), Version 23.0 or later. Medical/surgical history data will be summarized by system organ class (SOC) and preferred term (PT).

In addition to medical/surgical history collected at screening, listings will also include COVID-19 symptom onset date, COVID-19 vaccination history (including dates of administration and manufacturer), [REDACTED] date of diagnosis of ARDS, severity of ARDS at screening (per Berlin Criteria; ARDS Definition Task Force), date and time of initial intubation, and the date and time of initiation of mechanical ventilation. Protocol version will be included in these listings.

### **8.2.6. Prior and Concomitant Medications**

Listings and tabulations associated with Prior and Concomitant Medications will use the Safety Analysis Set.

All medications taken and procedures undergone during the study will be recorded. All medications will be coded using World Health Organization-Drug (WHO) Global B3 September 2020 or later.

Medications will be presented according to whether they are being taken prior to and/or during the study (concomitant). Prior medications are defined as those taken prior to the initiation of the IP. Concomitant medications are defined as those with a start date and time on or after the initiation of IP or those with a start date and time before the initiation of IP

that are ongoing or with a stop date/time on or after the initiation of IP. If medication date/time is incomplete and it is not clear whether the medication was concomitant, it will be assumed concomitant. For imputation of missing concomitant medication dates, please refer to Appendix A. Note that it is possible for a medication to be both ‘prior’ and ‘concomitant’ when a medication has start date and time before the initiation of IP and end date and time either missing or after the initiation of IP.

Concomitant procedures are recorded on a separate electronic case report form (eCRF) page; this will be presented in a listing by participant. The study day for the end date of the procedure will be provided, when a complete end date is available.

Concomitant medication data will be tabulated for the following classes of medications using a standard concomitant medication table format. Medications in the following categories will also be listed:

- CNS depressants (eg, benzodiazepines, opioids/opiates, barbiturates, propofol);
- other agents utilized for sedation effects (eg, dexmedetomidine);
- drugs administered to treat or prevent ICU delirium (eg, antipsychotics, atypical antipsychotics, or other agents intended for delirium treatment).

Please see Section 8.4.2 for details regarding the ATC Level 3 codes corresponding to these medication classes. There will be no prohibited medications defined for this study.

### **8.2.7. Investigational Product Exposure**

The total exposure (in mcg/kg) to IP is defined as the total mcg/kg for brexanolone that was received during the study. Total drug exposure for participants randomized to placebo is zero, unless the participant received brexanolone by mistake, in which case the total exposure comes from brexanolone exposure.

The exposure duration to IP is defined as total number of hours treated with study drug during the study, which is calculated as (end time of infusion – start time of infusion [in seconds])/3600. Note that this does not exclude the time when the dose has been interrupted.

The total exposure and exposure duration to IP will be summarized by descriptive statistics, using the Safety Analysis Set.

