### **10.5. Investigational Product Administration**

IP will be administered as a single, continuous, IV infusion for 60 hours. Initiation of the infusion must occur within 6 hours of randomization.

The specific infusion dose of IP will be calculated based on weight (obtained at screening) for each participant and will be administered as a single continuous IV infusion for 60 hours at 70 mcg/kg/h for 58 hours followed by a 2-hour taper at 35 mcg/kg/h. Placebo infusion rates will be matched to the brexanolone infusion rates.

Transfer out of the ICU is not an indication to discontinue the infusion of IP. The IP infusion may be stopped or the dose reduced due to an AE as described in Section 7.4.

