## 8. STATISTICAL ANALYSIS

### 8.1. General Considerations

Unless otherwise specified, continuous endpoints will be summarized with n, mean, standard deviation (SD), median, minimum (min) and maximum (max). The min and max will be reported with the same number of decimal places as the source (raw) data. Mean and median will be reported to 1 decimal place more than the source (raw) data and standard deviation will be reported to 2 decimal places more than the source (raw) data, but no more than 4 decimal places. Any values that require transformation to standard units (metric or SI) will be converted with the appropriate corresponding precision.

Categorical variables (eg, presence of an AE) will be summarized using counts and percentages. Percentages will be presented to 1 decimal place unless otherwise specified.

All participant data, including those derived, that support the tables and figures will be presented in the participant data listings. Some data may be presented only in participant data listing with an underlying table or figure; these will be indicated in relevant sections below.

All summaries will be provided by treatment – either by treatment assigned at randomization, or actual treatment received. Actual treatment is defined as:

- Brexanolone – if the participant was exposed to brexanolone;
- Placebo – if the participant received placebo and not a single dose of brexanolone.

For the purpose of all safety and efficacy analyses, baseline is defined as the last non-missing measurement on or prior to the initiation of IP, unless stated otherwise.

P-values will be reported to four decimal places, with p-values less than 0.0001 reported as “<0.0001”. P-values larger than 0.9999 will be reported as “>0.9999”.

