### **8.2.8. Investigational Product Adherence**

IP adherence (%) is calculated as [Actual total dose (in mcg/kg)/Planned total dose (in mcg/kg) x 100]. Actual total dose will account for the tapering period. IP adherence will be summarized using the Safety Analysis Set.

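### SAP 8.2.7 reports elapsed infusion time as hours treated, so pauses count as treatment; SAP 8.2.8 does not say how placebo dose enters adherence

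*SAP*

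**What the plan says.** **Duration.** SAP 8.2.7 states: "The exposure duration to IP is defined as total number of hours treated with study drug during the study". The formula that follows is end time minus start time of the infusion, in seconds, divided by 3600. The section then adds: "Note that this does not exclude the time when the dose has been interrupted".

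**Total exposure.** In the same section: "The total exposure (in mcg/kg) to IP is defined as the total mcg/kg for brexanolone that was received during the study". For the placebo arm: "Total drug exposure for participants randomized to placebo is zero". There is one exception: brexanolone given to a placebo participant in error is counted.

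**Adherence.** SAP 8.2.8 states: "IP adherence (%) is calculated as [Actual total dose (in mcg/kg)/Planned total dose (in mcg/kg) x 100", and summarizes the result on the Safety Set. It adds only that the actual dose takes the taper into account. It does not tie actual total dose to the total exposure of 8.2.7, and it gives no rule for placebo.

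**Related text.**
- Protocol 7.4 allows the infusion to be stopped, and resumed once symptoms resolve.
- Protocol 10.5 sets a 60-hour infusion and says: "Placebo infusion rates will be matched to the brexanolone infusion rates".
- Protocol 12.2.1 and SAP 5.1 both count placebo as IP.
- Protocol 13.6.1 promises a summary of TEAEs leading to IP discontinuation, dose reduction or study withdrawal. SAP 8.4.1 keeps discontinuation and withdrawal but does not mention dose reduction.

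**The concern.** Time with the pump stopped is not time on treatment, so the label in SAP 8.2.7 and its formula describe different quantities for anyone whose infusion was interrupted. Interruptions are foreseeable here. Protocol 7.4 provides for stopping because of unplanned sedation/somnolence or an intolerable related AE, and sedation is both an expected effect of the drug class and an AESI. How often and for how long infusions were stopped, by arm, is therefore useful tolerability information.

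As specified, the duration row cannot show it. In the readable SAP text no other table summarizes interruptions by arm, and the planned summary of TEAEs leading to dose reduction has been left out.

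Adherence is the other table that would reflect lost infusion time. Because the placebo dose is not defined there, two programmers could fill the placebo column differently, and the between-arm comparison would depend on which reading they chose.

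**Working it through.** The documents give no numerical duration, exposure or adherence result, so there is no figure to reproduce. The SAP formulas are applied below to the protocol regimen.

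**Inputs**
- Regimen (protocol 10.5): 70 mcg/kg/h for 58 h, then 35 mcg/kg/h for 2 h; 60 h in total.
- Planned total dose: 70 × 58 + 35 × 2 = 4060 + 70 = 4130 mcg/kg.
- Length of pause, x: not in the documents. Assumed values are 2, 6, 12 and 24 h, with the pause falling in the 70 mcg/kg/h period.
- Whether lost time is made up: protocol 7.4 permits resumption without saying that the infusion is extended, so both cases are shown.

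**Step 1. Duration**
- Case A, infusion completed late: reported 60 + x, infused 60, overstatement x/60.
- Case B, infusion ends at Hour 60: reported 60, infused 60 − x, overstatement x/(60 − x).

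| Pause (assumed) | A: reported / infused | A: overstatement | B: reported / infused | B: overstatement |
|---|---|---|---|---|
| 2 h | 62 / 60 h | 3.3% | 60 / 58 h | 3.4% |
| 6 h | 66 / 60 h | 10.0% | 60 / 54 h | 11.1% |
| 12 h | 72 / 60 h | 20.0% | 60 / 48 h | 25.0% |
| 24 h | 84 / 60 h | 40.0% | 60 / 36 h | 66.7% |

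In case A the pause lengthens the reported duration; in case B it leaves it unchanged. In neither does it shorten it. With pauses subtracted, a 6 h pause gives 60 h (A) or 54 h (B).

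**Step 2. Does adherence pick up the loss in the brexanolone arm?** It does when the lost time is not made up (case B): adherence = (4130 − 70x)/4130. This gives 96.6% at 2 h, 89.8% at 6 h, 79.7% at 12 h and 59.3% at 24 h. The duration formula does not distort it. In case A the full dose is given, so adherence is 100% and the pause appears in neither table as an interruption.

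**Step 3. Placebo adherence after a complete infusion**
- Actual dose read as the 8.2.7 exposure: 0/4130 = 0%.
- Planned dose also counted as brexanolone only: 0/0, undefined.
- Both taken as the nominal dose at matched rates: 4130/4130 = 100%.

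The exception for brexanolone given in error does not alter the placebo column. SAP 8.1 places a participant in the actual-treatment placebo group only "if the participant received placebo and not a single dose of brexanolone", so every Safety Set placebo participant has zero brexanolone exposure.

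**Step 4. Is the by-arm information planned elsewhere?** Protocol 13.6.1 lists three consequences of TEAEs to be summarized; SAP 8.4.1 carries over two. No readable part of SAP 6.1 records the removal of the third. Parts of the SAP are redacted and the list of displays in Appendix B is not visible, so this holds for the readable text only.

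**The case against.** The strongest case on the other side has four parts.

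**The convention is disclosed.** SAP 8.2.7 says openly that interrupted time is not excluded, so no programmer would compute the wrong quantity by accident. That is true, and this is not a hidden error. The output would still carry a label that its values do not meet, and disclosure in the SAP does not reach someone reading the table.

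**Placebo exposure of zero is right.** A reader might infer that the zero is itself a mistake, or that placebo adherence must come out as 0% or undefined. The documents support neither. Zero is correct for a quantity defined as brexanolone received. SAP 8.2.8 uses a different term that is never linked to 8.2.7, and with placebo counted as IP and infusion rates matched, the 100% reading is available. What stands is that the SAP does not say which reading applies.

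**Paused participants do not necessarily show more hours.** Reported duration rises above 60 h only if the infusion runs past Hour 60, which protocol 7.4 does not state. If it ends at Hour 60, paused and unpaused participants look the same. A permanent stop shortens the duration correctly.

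**Tolerability is captured elsewhere.** A reader might conclude that the formula masks a tolerability difference between the arms. That goes too far. Dose-based adherence falls when lost time is not made up, AESIs including excessive sedation are tabulated separately (SAP 8.4.1), TEAEs leading to treatment discontinuation are summarized, and the RASS values taken when the infusion is stopped or reduced are listed (SAP 8.4.6). What stands is narrower: duration cannot show interruptions, and no readable table summarizes them by arm.

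**Conclusion.** The point holds for duration. SAP 8.2.7 presents elapsed time as treated time, and for any participant with an interruption the two differ by the full length of the pause. The overstatement is about 3% for a 2 h pause, 10-11% for 6 h and 20-25% for 12 h. These pause lengths are assumptions, and the documents give no expected frequency of interruptions, so the effect on an arm-level mean cannot be estimated.

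The placebo part is a missing rule in SAP 8.2.8 and does not make the adherence formula wrong. The formula is sound for brexanolone participants.

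The importance is minor. Descriptive exposure, adherence and tolerability tables are affected; no efficacy endpoint, test or sample size changes.

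**What to change.** 1. In SAP 8.2.7, compute duration as end minus start minus recorded interruptions. If elapsed time is still wanted, keep it as a separate row labelled as elapsed infusion time.
2. Report the number of interruptions and their total length by arm on the Safety Set.
3. In SAP 8.4.1, restore the summary of TEAEs leading to dose reduction, or record its removal in SAP 6.1.
4. In SAP 8.2.8, state that actual and planned dose for placebo are the nominal amounts at the matched rates. Keep total brexanolone in mcg/kg as a separate row, where zero for placebo is correct.

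The cost is a few lines of SAP wording and minor programming before database lock. No new data collection should be needed: protocol 9.4 has sites record the time and dose of administration and any deviation from the regimen, and 10.6 requires reasons for departures. This assumes that stop and restart times reached the database. The actual dose in SAP 8.2.8 already depends on infusion times and rates, but this should be confirmed.

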### **8.2.8. Investigational Product Adherence**

IP adherence (%) is calculated as [Actual total dose (in mcg/kg)/Planned total dose (in mcg/kg) x 100]. Actual total dose will account for the tapering period. IP adherence will be summarized using the Safety Analysis Set.

## **8.3. Efficacy Analysis**

The Full Analysis Set will be used for all efficacy analyses. When referencing “Day 28” in efficacy analyses, it is understood that this refers to Visit 11.

### 8.3.1. Definition of Efficacy Endpoints

### 8.3.1.1. Proportion of participants alive and free of respiratory failure at Day 28

The primary efficacy endpoint is the proportion of participants alive and free of respiratory failure at Day 28. Respiratory failure is defined based on resource utilization, requiring at least one of the following:

- Endotracheal intubation and mechanical ventilation
- Oxygen delivered by high-flow nasal cannula (heated, humidified oxygen delivered via reinforced nasal cannula at flow rates >20 L/min with fraction of delivered oxygen  $\geq 0.5$ )
- Noninvasive positive pressure ventilation
- Extracorporeal membrane oxygenation (ECMO)

Please see Appendix D for a detailed breakdown of the Procedural terms used to identify subjects with respiratory failure.

### 8.3.1.2. All-cause mortality

The key secondary efficacy endpoint is the all-cause mortality, measured by proportion of participants who die due to any cause through Day 28.

### 8.3.2. Analysis of Primary Efficacy Endpoint

The primary efficacy endpoint is the proportion of participants alive and free of respiratory failure at Visit 11 (Day 28  $\pm$  3 days).

- If a participant dies prior to Visit 11, the participant will be assigned a value of “no” for the primary endpoint.
- Participants discontinuing the study for reasons other than death and prior to Visit 11 will not be included in the primary analysis.

The difference in the proportions between brexanolone and placebo will be analyzed using the SAS procedure GENMOD. In this model, the proportion will be the response variable, and the predictor variables will be treatment arm and age group (<70 or  $\geq$ 70 years).

Participants will be analyzed according to their actual age group, regardless of the age group used for randomization purposes. The proportion will be directly modeled using the binomial distribution with identity link. The point estimate, confidence interval, and p-value for the difference in the fitted proportions will be obtained using the “LSMEANS” statement to

 Lack of endotracheal intubation, for purposes of the Primary Efficacy Endpoint, does not require a subsequent  $>48$  hour period of time without need for reintubation or noninvasive ventilation.

produce estimated treatment differences (ie, differences in proportions). A sample SAS code is as follows:

```
proc genmod data=indata;
  class trt01p agegr1;
  model aval = trt01p agegr1 / dist=binomial link=identity;
  lsmeans trt01p / diff cl;
run;
```

Please see Appendix D for a detailed breakdown of the Procedural terms used to identify subjects with lack of respiratory failure.

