## 13. STATISTICS

Detailed description of the interim and final analyses to be performed in the study will be provided in the statistical analysis plan (SAP). To avoid a potentially biased estimate of the event rate in each arm at the time of the interim analysis, both the interim analyses and final analysis will incorporate all available data from all participants in the study in the analysis population, regardless of whether participants have reached Day 28. The SAP will be finalized and approved prior to database lock of the interim analysis. Any changes/additions to the SAP following database lock will be described in detail in the clinical study report.

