### 13.2. Handling of Missing Data

Every attempt will be made to avoid missing data. All participants, including those with missing data, will be used in the analyses, as per the analysis sets defined in Section 13.1. The primary analysis method will use all nonmissing data available. In addition, tipping-point analyses will be conducted as sensitivity analyses to assess the impact of missing data.

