### 13.5. Efficacy Analysis

The primary endpoint of proportion of participants alive and free of respiratory failure at Day 28 will be summarized using a logistic regression, adjusting for age group. The odds ratio and difference in proportions will be estimated. The secondary endpoint of all-cause mortality through Day 28 will be analyzed using both the Kaplan-Meier method for time to death and the logistic regression model for the proportion of deaths. [REDACTED]

[REDACTED] All efficacy summaries will be performed on the Full Analysis Set. In addition, if over 5% of randomized participants do not receive IP, a sensitivity analysis of the primary endpoint will be conducted on the Randomized Set.

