#### 6.1.4. Efficacy Analyses

Protocol Section 13.5 requires an odds ratio analysis of the primary endpoint and a Kaplan-Meier time to event analysis of the key secondary endpoint (all-cause mortality). Neither of these analyses will be performed.

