#### **6.1.5. Tipping Point Analyses**

Protocol Section 13.2 requires a set of tipping point analyses to assess the impact of missing data. This will not be done.

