### 8.3.3. Analysis of Key Secondary Efficacy Endpoint

The proportion of participants who died for any cause (all-cause mortality) by Visit 11 (Day  $28 \pm 3$  days) is the key secondary endpoint.

- If a participant dies prior to Visit 11, the participant will be assigned a value of “yes” for the key secondary endpoint
- Participants having Visit 11 (either in-person or via phone call) will be assigned a value of “no” for the key secondary endpoint
- Participants having follow-up assessments on/after Day 25 and known to be alive for those assessments and for whom Visit 11 was not performed will be assigned a value of “no” for the key secondary endpoint
- Participants with early study termination (ET) for reasons other than death and prior to Visit 11 will not be included in the primary analysis.

The difference in the proportions between brexanolone and placebo will be analyzed using the SAS procedure GENMOD. In this model, the proportion will be the response variable, and the predictor variables will be treatment arm and age group ( $<70$  or  $\geq 70$  years).

Participants will be analyzed according to their actual age group, regardless of the age group used for randomization purposes. The proportion will be directly modeled using the binomial distribution with identity link. The point estimate, confidence interval, and p-value for the difference in the fitted proportions will be obtained using the “LSMEANS” statement to produce estimated treatment differences (ie, differences in proportions). The sample SAS code presented in Section 8.3.2 will be adapted for this purpose.

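### Participants who leave alive before Visit 11 are excluded from both efficacy analyses, and the SAP drops the tipping-point check (both endpoints) and Kaplan-Meier (mortality) with no readable replacement

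*SAP*

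**What the plan says.** **Primary endpoint (SAP 8.3.2).** A death before Visit 11 counts as not meeting the endpoint. For those who leave alive: "Participants discontinuing the study for reasons other than death and prior to Visit 11 will not be included in the primary analysis".

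**Mortality (SAP 8.3.3).** A death before Visit 11 counts as an event. For the rest: "Participants with early study termination (ET) for reasons other than death and prior to Visit 11 will not be included in the primary analysis". The words primary analysis appear here in the key secondary section; I read them as meaning the mortality analysis. One exception is scored as not dead: "Participants having follow-up assessments on/after Day 25 and known to be alive for those assessments and for whom Visit 11 was not performed".

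**What the protocol planned.** Protocol 13.2: "The primary analysis method will use all nonmissing data available. In addition, tipping-point analyses will be conducted as sensitivity analyses". Protocol 13.5, for mortality only: it "will be analyzed using both the Kaplan-Meier method for time to death and the logistic regression model for the proportion of deaths". Protocol 13, after giving avoidance of bias at the interim as its purpose, says of both the interim and the final analysis that the "final analysis will incorporate all available data from all participants in the study in the analysis population, regardless of whether participants have reached Day 28".

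**What the SAP removes.** SAP 6.1.4 names the odds ratio for the primary endpoint and Kaplan-Meier for mortality: "Neither of these analyses will be performed". SAP 6.1.5: "Protocol Section 13.2 requires a set of tipping point analyses to assess the impact of missing data. This will not be done". SAP 6.1 attributes the drops to the sponsor's early termination, on grounds of simplicity or because the analyses were no longer tenable.

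**The concern.** The rule is asymmetric in time. A participant who dies on Day 5 stays in numerator and denominator. One who leaves alive on Day 5 is removed from both, although the first five days of survival were observed. Deaths known on study therefore weigh too heavily in a mortality proportion, even if leaving has nothing to do with prognosis. A death after withdrawal falls under the exclusion, so the rule captures deaths on study rather than all deaths by Day 28.

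For the primary endpoint, a nonmissing-data analysis is what Protocol 13.2 allows. What has gone is the sensitivity analysis planned with it. For mortality two things have gone: that sensitivity analysis, and the one planned method that uses survival time up to withdrawal. The readable SAP has no imputation, bounding or censored analysis for either endpoint.

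At stake is whether a reader of the final report can tell how far the result depends on the excluded participants. The trial stopped early for recruitment reasons, so each missing outcome may weigh more than planned.

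**Working it through.** **1. The plan's own figure.** Inputs from SAP 5.2: 50% v 77%, two-sided alpha 0.05, chi-square, 80% power. With mean proportion 0.635, n per arm = [1.960·√(2·0.635·0.365) + 0.842·√(0.5·0.5 + 0.77·0.23)]² / 0.27² = 48.7, so 49 per arm and 98 in total, against about 100 stated. Power at 50 per arm is 81.0%. The readable text has no dropout allowance; excluding 5% (47.5 per arm) gives 79.0%.

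**2. Withdrawal unrelated to outcome.** The documents give no dropout rate and no mortality assumption, so these inputs are assumed: true 28-day mortality d = 40%, and latent dropout by Day 28 of c = 5%, 10% or 20%. True response p = 50% is the SAP's placebo rate. With constant hazards λ = −ln(1−d)/28 and γ = −ln(1−c)/28:

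- completers K = (1−d)(1−c)
- observed deaths D = λ/(λ+γ)·(1−K)
- share leaving alive L = γ/(λ+γ)·(1−K)
- mortality under the SAP rule = D/(D+K)
- response under the SAP rule = p(1−c)/(D+K)

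| c | K | D | L | Mortality | Response |
|---|---|---|---|---|---|
| 0% | 0.600 | 0.400 | 0% | 40.0% | 50.0% |
| 5% | 0.570 | 0.391 | 3.9% | 40.7% | 49.4% |
| 10% | 0.540 | 0.381 | 7.9% | 41.4% | 48.8% |
| 20% | 0.480 | 0.362 | 15.8% | 43.0% | 47.5% |

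Kaplan-Meier gives 40.0% throughout, because here censoring is independent of death.

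**3. Equal dropout, between-arm difference.** Placebo as above. Brexanolone response is 77%; mortality is set so that the same share of non-responders die: 0.23 × 0.40/0.50 = 18.4%. The 27-point difference becomes 27.2, 27.4 and 27.8 points at c = 5%, 10% and 20%.

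**4. Dropout in one arm only, no true effect.** With nobody leaving one arm and 15.8% leaving the other alive, the false difference is 43.0 − 40.0 = 3.0 points for mortality and 50.0 − 47.5 = 2.5 points for response. At 50 per arm the standard errors are √(2·0.24/50) = 9.8 and √(2·0.25/50) = 10.0 points, so the shifts are about 0.3 and 0.25 of a standard error.

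**5. Outcome-related withdrawal.** Half the participants have 20% mortality and half 60%, so the truth is 40%. The SAP rule averages D and K over the two halves. Kaplan-Meier tends to 1 − exp(−∫h(t)dt) over 28 days, where h(t) is the mean death hazard among those still at risk.

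| Latent dropout (good / poor prognosis) | Leave alive | SAP rule | Kaplan-Meier |
|---|---|---|---|
| 30% / 10% | 16.8% | 44.7% | 41.2% |
| 10% / 30% | 14.6% | 41.5% | 38.8% |

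Kaplan-Meier is closer to 40% in both rows but is not unbiased in either.

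**6. Bounds.** With k of N missing per arm and difference x among completers, opposite extreme assignments give x(1 − k/N) ± k/N.

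- x = 0: ±2 points (k = 1) or ±4 points (k = 2) at N = 50; ±5 or ±10 points at an assumed N = 20.
- x = 27 points, N = 50: k = 2 gives 25.9 ± 4, or 21.9 to 29.9 points; k = 5 gives 24.3 ± 10, or 14.3 to 34.3 points.

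**The case against.** The case for leaving the SAP alone has real force. The dropped analyses are named, tied to their protocol sections and explained. The primary rule agrees with Protocol 13.2. The summary measure is the between-arm difference, which hardly moves under equal dropout, and even the one-sided case in step 4 is well under one standard error. Protocol 8.4.1 keeps participants in follow-up after treatment stops, so the number excluded may be zero. All of that stands and limits the size of the point.

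It does not remove the point. Protocol 8.4 allows withdrawal at any time and 8.4.3 defines loss to follow-up, so exclusions are possible. Early termination does not explain why a survival curve or a bounding table could not be produced from fewer participants: Protocol 11.1.7 already collects date and time of death.

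Four stronger readings are tempting, and the documents do not support them.

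- *The primary endpoint lost two safeguards.* It lost one. Kaplan-Meier was planned in Protocol 13.5 for mortality only, beside logistic regression, and is not presented as a missing-data method.
- *The exclusion breaks the SAP's own estimand.* SAP 4.1.3 commits to data observed on study. A participant who left early has no observed Day 28 status, and study withdrawal is not among the examples of intercurrent events.
- *Readers could not bound the effect.* SAP 8.2.1 tabulates withdrawals with reasons, so an approximate bound can be built by hand.
- *The SAP plainly contradicts Protocol 13.* That sentence does name the final analysis, but its stated purpose is the interim, since cancelled. The mismatch is real for mortality, where survival time before withdrawal goes unused, but it is a secondary argument.

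**Conclusion.** The concern holds in limited form. The SAP keeps deaths known on study, removes live withdrawals, and drops the planned check on that choice for both endpoints, and Kaplan-Meier for mortality. The per-arm mortality proportion is then biased upward whenever someone leaves alive for reasons unrelated to outcome: by 1.4 to 3.0 points when about 8% to 16% leave alive, given an assumed true 40% and constant hazards. Under outcome-related withdrawal the size depends on who leaves.

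A reader might infer that the treatment comparison itself is materially biased. That cannot be concluded. Equal dropout moves 27 points by at most 0.8; unequal or outcome-related dropout can move it in either direction; with no exclusions nothing changes. The documents give no dropout count or final sample size, so every rate above is illustrative. Nor is anything concealed: the drops are stated openly. That no replacement exists can be said only of the readable text, since parts of SAP 6.1 and 8.3 are redacted. This is a worthwhile, inexpensive repair, not a flaw that invalidates the analysis.

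**What to change.** Keep the SAP 8.3.2 model as the primary analysis. Before database lock:

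1. Add a best/worst-case or tipping-point table for the primary and mortality endpoints in the Full Analysis Set, showing the number excluded per arm. This covers both endpoints and makes no assumption about why people left.
2. Restore Kaplan-Meier Day 28 mortality by arm, censoring live withdrawals at last contact and stating that censoring is assumed non-informative. This helps mortality only and does not cure outcome-related withdrawal (step 5), so it does not replace the first item.

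The cost is a few extra tables and some SAP wording, with no new data. If nobody was excluded, the first table is empty, and saying so settles the matter.
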